2.4.2.1 Target effect sizes we aim at detecting

In this subsection, we select one PA outcome (MVPA min/day) and one dietary outcome (fruit and vegetable intake g/day) to illustrate how we estimate the target effect sizes from the existing literature.

For MVPA minutes per day, we use an estimate of the standard deviation (SD) of MVPA minutes based on HeadUp's existing UK users who signed up in 2019, similar in demographic and socioeconomic status to those of the target groups (SD = 26 min/day, n = 19,898 users). A systematic review³⁹ of RCTs testing the impact of financial incentive intervention on PA suggested a wide range of effect sizes (from 0.02 to 0.4 SD units). We consider the midpoint of this range to be a plausible estimate of expected effect size, therefore aim to have a minimum detectable effect size (MDES) of 0.2 SD units, or a difference of 5.2 MVPA min/day (36 MVPA min/week) between intervention (any incentive) and control (no incentive) groups.

For daily fruit and vegetable intake (g/day), we obtained an SD estimate from the National Diet and Nutrition Survey data (NDNS, 2020)⁴⁰, corresponding to adults from England, 19-64 years old (SD = 190g /day, n = 475). Previous meta-analysis⁴¹ suggests that the effect size of interventions designed to increase adults' consumption of fruit and vegetables is in the 0.1 ~ 1.2 serving / day range (corresponding to 8 ~ 112 g/day). We assumed a more modest target effect size of 0.11 SD units, or a difference of 21 g/day.

³⁹ Mitchell et al. (2020)

⁴⁰ Public Health England. (2021). National Diet and Nutrition Survey: Diet, nutrition and physical activity in 2020 - a follow-up study during COVID-19. Retrieved from

https://www.gov.uk/government/statistics/ndns-diet-and-physical-activity-a-follow-up-study-during-covid-19

⁴¹ Pomerleau, J., Lock, K., Knai, C., & McKee, M. (2005). Interventions Designed to Increase Adult Fruit and Vegetable Intake Can Be Effective: A Systematic Review of the Literature. *The Journal of Nutrition*, *135*(10), 2486–2495. doi: 10.1093/jn/135.10.2486

Table 5. Minimum sample size required at the analysis stage (post-attrition) given the target effect sizes from literature review.

Summary	mary Physical activity		Diet			
Primary outcome measure	MVPA minutes per day	Daily steps	Daily fruit and vegetable intake	Daily fibre intake	Free sugars (% food energy)	Saturated Fat (% food energy)
Standard deviation data source	n = 19,898 UK users, whose demographic and obesity profiles are most similar to the target population of this trial ⁴² (HeadUp Labs, 2019)		n = 475 UK adults (19-64 years old) ⁴³ (National Diet and Nutrition Survey 2020)			
Standard deviation estimate	26 min/day	4,096/day	190 g/day	7.5 g/day	6.3 %	3.2 %
Effect size range from prior literature	0.02 to 0.4 SD units ⁴⁴		0.04 to 0.58 SD units ⁴⁵			
Target minimum detectable effect size in SD (MDES)	0.2 SD units		0.11 SD unit			
Target MDES in absolute terms (note: these are all larger than the effect size we estimate to be powered for)	5.2 MVPA min/day	819 steps/day	21 g/day	0.83 g/day	0.69 %	0.35 %
Assumed attrition rate	See Table 7 (Section 2.4.2.3)					

⁴² We only included user whose age profile matches that of the target population, i.e. 18-65 years old, and 69% of the included users were overweight or obese, highly comparable to the proportion in Wolverhampton, which is 70% according to the UK's latest obesity statistics report.

⁴³ Public Health England. (2021). National Diet and Nutrition Survey: Diet, nutrition and physical activity in 2020 - a follow-up study during COVID-19. Retrieved from https://www.gov.uk/government/statistics/ndns-diet-and-physical-activity-a-follow-up-study-during-covid-19

⁴⁴ Mitchell et al. (2020). Financial incentives for physical activity in adults: systematic review and meta-analysis. *British Journal of Sports Medicine*, 54(21), 1259-1268.

⁴⁵ Pomerleau, J., Lock, K., Knai, C., & McKee, M. (2005). Interventions Designed to Increase Adult Fruit and Vegetable Intake Can Be Effective: A Systematic Review of the Literature. *The Journal of Nutrition*, *135*(10), 2486–2495. doi: 10.1093/jn/135.10.2486

Adjustment for baseline covariates	Corr. coef = 0.25-0.75 (0.5 as most realistic)			
Target power	80%			
Adjusting for multiple comparisons	Bonferroni adjustment ⁴⁶ for primary outcomes by category (one comparison each of all incentive arms [pooled] vs. control; the number of adjustments is 2 for PA activities and 4 for dietary outcomes)			
Allocation ratio across arms post-attrition	3 participants in the control arm for every 1 participant in each intervention arm			
Cluster size assumptions for household-level randomisation	Sample will comprise: 39% 1-adult HHs, 41% 2-adult HHs, and 20% 3-adult HHs, with all adults in a HH signing up			
Assumed ICC (more details in Appendix B)	0.2-0.5 (0.2-0.4 as more realistic)			
Number of overall users required for smaller dietary outcome target MDES at the 5m mark analysis stage	4,200 (2,100 in control; 700 per intervention arm)			

⁴⁶ The Benjamini-Hochberg false discovery adjustment will be applied during analysis of primary outcomes, but as it is not possible to apply this before having the data, the more conservative Bonferroni adjustment provides an upper bound on power here.

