2.4 Sample size and minimum detectable size

2.4.1 Summary

The trial will adopt **a household-level randomisation**, with a target sample size of **around 4,200 participants** (2,100 in the control arm, 700 per intervention arm) at the final data collection point (**5 months after the randomisation**) to be powered to detect effect sizes deemed substantive from previous literature (see Section 2.4.2.2 Table 5). We expect users to come from ~2,300 households based on the demographic profile of Wolverhampton LA (see Appendix B).

To achieve a post-attrition sample of 4,200 participants, HUL expects to recruit a sample of around **25,800 participants** at the beginning of the baseline stage, given the attrition rate at various trial stages estimated by HUL (see Section 2.4.2.3 Table 6).

BIT has conducted power calculations for the primary research question "Does the incentive scheme improve physical activity (PA) and diet at the five month mark?". The power calculations focus on the primary outcomes. The primary analysis pools all the treatment arms together and assesses their overall difference against the control.

Given the post-attrition sample size of 4,200 participants, the minimum effect sizes we are powered (at 80% level) to detect at the 5-month's mark in the primary analysis are:

Physical activity primary outcomes:

- Daily MVPA (min/day): 2.4 min/day
- Daily steps: 371 steps/day

Dietary primary outcomes:

- Fruit and vegetables (g/day): 18.7 g/day
- Fibre (g/day): 0.74 g/day
- Free sugars (% food energy): 0.63%
- Saturated Fat (% food energy): 0.31%

The following subsections provide details on the key assumptions and decisions made concerning the power calculation. First, we provide the minimum required sample size at the analysis stage (post-attrition) given the target effect sizes for the primary outcomes (see Table 5). Then, we show the minimum required sample size at the recruitment stage (pre-attrition) given the predicted attrition rate at various stages (see Table 6) based on HUL's estimations. Last, we calculate the minimum detectable effect size for primary outcomes (see Table 7) based on the target sample size confirmed as feasible for this project by HUL and DHSC.

For further information on specific assumptions behind household-level randomisation, multiple-comparisons-adjustment, inclusion of covariates, and allocation ratio among trial arms, please see Appendix B.

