⁵⁰ In using Intake24 questionnaire, we will strike a balance between maximising the validity and reliability of the method (Intake24 is used for the National Diet and Nutrition Survey) whilst minimising the burden on participants (more robust measures of dietary intakes, such as food diaries would be much more time-consuming). Based on previous studies, the user experience of completing Intake24 is generally positive. Feedback from participants in the field test of Intake24 suggests that the majority of people found the system user-friendly, enjoyable to use, and felt it accurately captured their diet. ⁵¹ It is our assessment that two recalls is a reasonable mid-point between the single administration recommended by the National Cancer Institute and the four recalls used by PHE's NDNS and in the original validation study. Four recalls would force us to extend the sign-up onboarding period of at least one week, with significant risks to the retention of users in the programme as it would involve asking participants to complete 80 minutes of questionnaire at each measurement time point. ⁵² The Intake24 team at Cambridge reassured BIT that it is not necessary that each user provides a recall for a weekday and one for the weekend for obtaining robust results. This is because it is only necessary that across the whole sample some users will provide some recalls for weekdays and some for weekends. As different users are nudged to provide a recall on different days, based on when they begin the onboarding phase, it is reasonable to expect that overall some recalls will reflect weekday dietary behaviour and some recalls weekend dietary behaviour.

Data collection point	Data collection method for dietary outcomes	Data collection method for PA outcomes

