- *missing. baseline*_{*ijd*} is a dummy variable that equals 1 if *baseline*_{*ijd*} is missing and 0 otherwise and will capture whether MVPA is systematically different for individuals who are missing baseline data for the same day;
- X_{ij} are individual level (including age, sex, ethnicity, education, BMI at baseline, and brand of wearable) and family level covariates we will take missing values for these covariates as separate categories rather than imputing;
- δ_{c_j} are the cluster (i.e. household) level random effects, which have mean zero and follow a normal distribution;
- For each family *j*, $\delta_{p_{ij}}$ are the individual (person) level random effects, which have mean zero within each household and follow a normal distribution;
- u_{ijd} is an idiosyncratic error term. We will use a compound symmetry covariance structure (default for a model with random intercepts).

The primary outcomes for diet are:

- Fruit and vegetables (g/day);
- Fibre (g/day);
- Free sugars (% daily food energy);
- Saturated fat (% daily food energy);

as self-reported in Intake24 recalls at the 5-month follow-up point. We will use a similar model to analyse this outcome, as shown below:

(2)
$$y_{ij} = \alpha + \beta Treatment_{j} + \gamma_{D} weekday_{ij} + \gamma_{W} week_{ij} + \gamma_{N} num. admin_{ij} + \dots \gamma_{B} baseline_{ij} + \gamma_{A} weekday. baseline_{ij} + \gamma_{X} X_{ij} + \delta_{Cj} + u_{ij}$$

$$\delta_{cj} \sim N(0, \sigma_c^2)$$
 for all j; $u_{ij} \sim N(0, \sigma_u^2)$ for all i, j

where:

- y_{ij} is person *i*'s energy intake according to Intake24 surveys at 5 months. If the person took two surveys, we average their reports;
- weekday_{ij} is the proportion of administrations at 5 months that occurred on a weekday (rather than on the weekend). For example, if an individual had one administration on Monday and one on Saturday, weekday. ind_{ij} equals 0.5. This is intended to account for the difference in dietary patterns between

weekdays and the weekend;

- *num. admin*_{ij} is the number of administrations at 5 months (1 or 2);
- baseline_{ij} is calculated in an analogous way to y_{ij}, but for the administration(s) at baseline;
- *weekday.baseline*_{ij} is calculated in an analogous way to *weekday*_{ij}, but for the administration(s) at the baseline;

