Adults per household	Number of households	% of total (102,177 households)		
1	39,777	39%		
2	41,784	41%		
3+ *	20,616	20%		
* set to 3 for simplicity in estimations as Census 2011 data does not provide further granularity				

* set to 3 for simplicity in estimations as Census 2011 data does not provide further granularity

Adjusting for multiple comparisons

For the primary outcomes, we will adjust for multiple comparisons using the Benjamini-Hochberg procedure within the physical activity outcomes (2 comparisons) and dietary outcomes (4 comparisons) separately. For the exploratory outcomes and questions, we will adjust for multiple comparisons separately within each research question and separately for physical activity and dietary outcomes. For example, when examining effects after 1 month on the primary outcomes, we will perform 2 comparisons for the physical activity outcomes and 4 for the dietary outcomes. We will do the same for the analysis at 3 months.

Baseline measures and other covariates

We assume that the inclusion of covariates such as baseline calorie intake, baseline MVPA min/day, socio-demographic information, and anthropometric information will reduce variance in the outcome measures, and therefore increase power. Based on prior research, the pre-post correlation in the calorie intake measure using Intake24 is expected to be ~0.5; for the measure of MPVA min/day this is expected to be ~0.8.⁹² Therefore, we conservatively assume that a correlation coefficient of at least 0.5 is realistic in this trial.⁹³

⁹² https://www.ncbi.nlm.nih.gov/pmc/articles/PMC6722486/;

https://journals.humankinetics.com/view/journals/jpah/8/5/article-p668.xml

⁹³ Note that our estimates are additionally conservative because we do not explicitly factor in multiple measurements per participant during both baseline and outcome timepoints (e.g. participants will be asked to complete two Intake24 measurements during baseline, and will be asked to wear the wearable device every day). We have chosen to not factor this in due to the uncertainty around compliance with the Intake24 and daily wearing of the wearable devices.

Appendix C - Recommended dietary intake according to the Recommended dietary intake according to the Government Dietary Recommendations

Outcome	Current intake	Desired change
Carbohydrates	212 g/day	Increase
Free sugars	51 g/day	Reduce
Total Fat	69 g/day	Met
Saturated fat	25 g/day	Reduce
Fibre	18 g/day	Increase

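### The dietary SDs come from a survey the protocol describes as using four recalls, while the trial outcome uses one or two; unless the recall basis is matched, the stated dietary minimum detectable effects are not assured at 80% power

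*Protocol*

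**What the plan says.** - **SD source.** Section 2.4.2.1 says of fruit and vegetables "we obtained an SD estimate from the National Diet and Nutrition Survey data (NDNS, 2020"), and gives "SD = 190g /day, n = 475". Table 5 takes all four dietary SDs (190 g/day, 7.5 g/day, 6.3%, 3.2%) from the same survey.
- **Recalls in the source.** Footnote 51 (Section 2.6.1.1) justifies two recalls as lying between "the single administration recommended by the National Cancer Institute and the four recalls used by" NDNS.
- **Recalls in the trial.** Section 2.6.3.5, equation (2), defines the outcome: "If the person took two surveys, we average their reports". The number of administrations may be 1 or 2, and Section 2.6.3.2 says a missing second recall is not imputed.
- **Power claim.** Section 2.4.1 lists "the minimum effect sizes we are powered (at 80% level) to detect at the 5-month's mark": 18.7 g, 0.74 g, 0.63% and 0.31% for diet. Table 7 repeats them.
- **Multiplicity.** Table 5 plans a "Bonferroni adjustment", where "the number of adjustments is 2 for PA activities and 4 for dietary outcomes".
- **Margin claimed.** Footnote 93 (Appendix B) says "our estimates are additionally conservative because we do not explicitly factor in multiple measurements per participant", and names the two Intake24 recalls as an example.

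**The concern.** A person's mean over four days carries less day-to-day noise than a mean over two, and much less than a single day. An SD taken across four-recall person means would therefore understate the SD of the trial endpoint. An SD quoted on 475 adults reads most naturally as an SD across persons, so the risk is real. Footnote 93 would also need checking. It treats repeated recalls as uncredited margin, but a four-recall SD would already contain more averaging than the trial will achieve.

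The dietary outcomes set the 4,200 target. The rule in Table 2 for relying on 3-month data is tied to 80% of that number, described as the sample needed for the Table 7 effects. If the dietary sensitivity is overstated, a null dietary result will be read as excluding effects that the trial could easily have missed.

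**Working it through.** **1. Reproducing the plan's figures.** Inputs: 2,100 v 2,100 (Section 2.4.1); ICC 0.3 and baseline correlation r = 0.5 (Section 2.4.2.2); mean household size 0.39×1 + 0.41×2 + 0.20×3 = 1.81 (Table 5); 80% power; alpha 0.05/4 = 0.0125. A two-sided 0.05 is assumed, as the protocol does not state it.

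Design effect = 1 + 0.81×0.3 = 1.243.

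MDES = (2.498 + 0.842) × sqrt(2/2100) × SD × sqrt(1.243 × 0.75)

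| Outcome | SD | Computed | Stated |
|---|---|---|---|
| Fruit and vegetables | 190 g | 18.9 g | 18.7 g |
| Fibre | 7.5 g | 0.746 g | 0.74 g |
| Free sugars | 6.3% | 0.627% | 0.63% |
| Saturated fat | 3.2% | 0.318% | 0.31% |

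The stated values follow from the unadjusted NDNS SDs. With the other inputs held, they have no slack.

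**2. Changing the recall basis, if the SDs are four-recall means.** Let rho be the reliability of one recall and q the share of users giving two. Assume the same mix at baseline and 5 months, and no true within-person change over time. In units of single-recall variance:

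- trial outcome variance: v = rho + (1 − rho)(1 − q/2)
- four-recall variance: v4 = rho + (1 − rho)/4
- pre-post correlation on the trial's basis: r = rho/v
- net inflation of the residual SD: t = sqrt(v/v4) × sqrt[(1 − r²)/0.75]
- power at the stated MDES: Φ(3.339/t − 2.498)
- fruit and vegetable MDES: 18.7 × t

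The correlation has to move with the SD, because averaging changes both. Taking the plan's 0.5 as a two-recall correlation gives rho = 0.33 (0.33/0.67 = 0.5). Taking it as a single-recall correlation gives rho = 0.5.

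| rho | Share giving two | sqrt(v/v4) | r | t | Power | MDES |
|---|---|---|---|---|---|---|
| 0.33 | all | 1.155 | 0.50 | 1.155 | 65% | 21.6 g |
| 0.33 | none | 1.414 | 0.33 | 1.540 | 37% | 28.8 g |
| 0.5 | all | 1.095 | 0.67 | 0.943 | 85% | 17.6 g |
| 0.5 | 85% | 1.122 | 0.63 | 1.001 | 80% | 18.7 g |
| 0.5 | half | 1.183 | 0.57 | 1.121 | 68.5% | 21.0 g |
| 0.5 | none | 1.265 | 0.50 | 1.265 | 56% | 23.7 g |

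The half-and-half row becomes 69.0% if the residual variances of the two groups are averaged instead: (0.943² + 1.265²)/2 = 1.244, so t = 1.116. The same factor t applies to the other three outcomes if they share the same rho.

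**3. If the SDs are single-recall SDs.** No inflation is needed. The stated values hold, and second recalls make them conservative.

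**4. Margin elsewhere.**
- The 21 g/day target that sized the trial tolerates 21/18.9 = 1.11, about an 11% larger residual SD.
- With no household clustering the MDES is 18.9/sqrt(1.243) = 17.0 g.
- Benjamini-Hochberg can at best test an outcome at 0.05: 18.9 × (1.960 + 0.842)/3.339 = 15.9 g.

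**The case against.** A reader might infer that the SDs are shown to be four-recall SDs and that dietary power is therefore clearly below 80%. The protocol does not support that. The four-recall remark is a general description of NDNS, made when discussing participant burden. The SDs come from a specific 2020 follow-up study, and the protocol does not say how many recalls it obtained or whether the SD is per person or per recall.

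Nor does a larger SD by itself settle the direction. If 0.5 is a single-recall correlation, two-recall averaging raises it to 0.67, and that gain outweighs the larger SD, so power is 85%. Footnote 93 is attached to the sentence on the correlation and covers both baseline and outcome measurements. In that case it is right for diet, and a reader should not conclude that it is simply reversed.

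There are other cushions. The analysis uses Benjamini-Hochberg, which gains power when several dietary outcomes move together but little when only one does. Full household sign-up is a deliberately conservative assumption. Second recalls are prompted and paid for, so the scenario with no second recalls is an extreme.

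All of this stands as a limit on the size of the problem. It does not remove the mismatch. The recall basis of the SDs is unstated, nothing is adjusted, and several plausible combinations fall well short of 80%. The 0.5 is also documented for calorie intake, not for these four outcomes.

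**Conclusion.** The point holds conditionally. The protocol sets SDs from a survey it describes as four-recall beside an endpoint of one or two recalls, without stating or reconciling the basis. If the SDs are four-recall person means, power at the stated dietary effects runs from about 37% (rho 0.33, one recall each) to about 85% (rho 0.5, two recalls each). At rho 0.5, 80% is kept only if roughly 85% or more of users give two recalls. At rho 0.33, it is not reached even if all do.

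These figures rest on an assumed rho, a common recall mix at both time points, no true within-person change, Bonferroni for four outcomes and ICC held at 0.3. They do not show that the trial is underpowered. They show that the 80% statement is not secured by the inputs given. The arithmetic from those inputs is sound.

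**What to change.** 1. Establish and state how many recalls underlie each NDNS SD in Table 5.
2. Put both the SD and the pre-post correlation on the one-to-two-recall scale, either from recall-level data or by the formulae above over a stated range of rho and two-recall completion.
3. Restate the four dietary MDES at n = 4,200 in Section 2.4.1, Table 5 and Table 7.
4. Keep footnote 93's claim of extra conservatism for diet only if the recalculation supports it.

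Keep the sample size. The cost is a re-run of the power calculation and some wording, with no extra participants or data. The downside is that the stated dietary MDES may become somewhat larger.

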2.4.2.2 Minimum required sample size at the analysis stage

Given the target effect size for PA and dietary outcomes, and under the assumptions of household ICC of 0.3, a baseline covariate correlation coefficient of 0.5, we estimate that achieving the targeted MDES requires a post-attrition sample size of **4,200 users (2,100** in the control arm, **700** per intervention arm) at the final data collection point, i.e. 5 months after the randomisation (see Table 6 for details).

2.4.2.3 Minimum required sample size at the participant recruitment stage

The minimum required sample size at the analysis stage is not necessarily the sample we need at the participant recruitment stage. An important consideration is the proportion of participants who are expected to drop out of the study post-randomisation and for whom we will not have any outcome data (i.e. *the attrition rate*). To have a well-powered sample for analysis requires setting recruitment targets that are substantially higher to account for this attrition during the trial. In their acquisition plan, HUL estimated the attrition rates by treatment conditions (see Table 6 for details).

Trial arm				Estim	ates				
	N at the beginning of the baseline period	N at the end of the baseline period (at randomisation)	Attrition rate at 1m mark	N needed at 1m mark	Attrition rate at 3m mark	N needed at 3m mark	Attrition rate at 5m mark	N needed at 5m mark	Attrition from the beginning of the baseline period to the 5m mark
High incentive	~3,100	~1,900	18%	1,550	44%	1,050	62%	700	77%
Medium incentive	~3,200	~1,950	18%	1,600	45%	1,100	63%	700	78%
Low incentive	~3,800	~2,250	21%	1,800	50%	1,150	69%	700	81%
Control group	~15,700	~9,400	26%	6,950	60%	3,800	78%	2,100	87%
Total	~25,800	~15,500	-	~11,900	-	~7,100	-	4,200	-
Note: Attrition rate between baseline and randomisation: 40% for all groups									

Table 6. Estimated sample size required at various trial stages given the corresponding estimated attrition rate

This is consistent with systematic reviews of digital health interventions showing attrition rates of up to 80% in some RCTs (*average* attrition is 40-50%), and a common indication of differential attrition between trial arms.⁴⁷

Based on the estimated attrition rate, HUL and DHSC agreed on a target sample size of **25,800** (3,100 in the high incentive group; 3,200 in the medium incentive group; 3,800 in the low incentive group; 15,700 in the control group) **at the beginning of the baseline phase.**

⁴⁷ Meyerowitz-Katz et al. (2020); Howarth et al. (2018); Beleigoli et al. (2019).

